3 OBJECTIVES AND ENDPOINTS

OBJECTIVES	HYPOTHESES	ENDPOINTS	JUSTIFICATION FOR ENDPOINTS
Primary			
To determine if NMES+ECC will maximize quadriceps strength symmetry better than the NMES placebo + ECC placebo at 9 months and 18 months post-ACL reconstruction (ACLR).	Participants receiving NMES+ECC will have greater quadriceps strength symmetry at 9 and 18 months post-ACLR when compared with the other 2 study arms.	
Co-primary endpoints:
 
 Change from baseline to 9 months post-ACLR in isokinetic quadriceps strength symmetry index. Change from baseline to 18 months post-ACLR in isokinetic quadriceps strength symmetry index. 	This trial is designed to evaluate whether NMES and ECC can improve quadriceps strength. Thus, quadriceps strength at 9 months (when participants return to activity) and 18 months (longer-term assessment) are the primary endpoints for the trial.
Secondary			
Secondary Objective 1: To determine if NMES+ECC will limit negative changes in cartilage health, defined as decreased proteoglycan cartilage density measured with T1rho or increased cartilage matrix degradation measured with T2 mapping in relation to the contralateral side, at 18 months following ACLR.	Participants in the NMES+ECC group will have significantly lower T1rho and T2 values in the injured knee compared to the uninjured knee, indicating greater proteoglycan density and less cartilage matrix degradation. Further, we would expect larger (injured/uninjured) ratios for both T2 and T1rho in the NMES placebo + ECC placebo group when compared to the NMES + ECC group. Ratios greater than 1.0 would indicate less proteoglycan density (T1rho) and greater matrix degradation (T2).	
 T1 relaxation ratio at 18 months post-ACL T2 relaxation ratio at 18 months post-ACL 	T1 and T2 relaxation times have been able to show early change in cartilage after ACLR and are sensitive to change in cartilage when the gold standard X-ray does not yet reveal change.

OBJECTIVES	HYPOTHESES	ENDPOINTS	JUSTIFICATION FOR ENDPOINTS
Secondary Objective 2: To determine if NMES+ECC will maximize biomechanical symmetry and physical function better than the placebos at 9 months and 18 months post-ACL reconstruction (ACLR).	Participants receiving NMES + ECC will have greater knee flexion angle and moment symmetry, higher scores on the KOOS, and larger distances hopped on the crossover hop and single-legged hop at 9 and 18 months when compared with other 3 study arms.	
 Knee joint flexion angle and moment at 9 months post ACLR Knee joint flexion angle and moment at 18 months post ACLR Score on KOOS at 9 months post-ACLR Score on KOOS at 18 months post-ACLR Distance hopped during cross-over hop and single-legged hop for distance at 9 months post-ACLR Distance hopped during cross-over hop and single-legged hop for distance at 18 months post-ACLR 	Knee flexion angle and moment are sensitive to changes in quadriceps strength. KOOS is a validated and reliable scale to assess patient-perceived function after ACLR. Distance hopped during the cross-over and single-legged hop for distance are standard clinical hop tests used after ACLR.
Exploratory Objective: To assess the ability of reducing the intensity of NMES and ECC to achieve a “true” placebo by comparing the NMES placebo + ECC placebo to the SOC Control group.	Participants receiving NMES placebo + ECC placebo will have similar change to those in the SOC control group from baseline to 9 months and to 18 months post-ACLR in isokinetic quadriceps strength symmetry index.	
 Change in isokinetic quadriceps strength symmetry index from baseline to 9 months post-ACLR Change in isokinetic quadriceps strength symmetry index from baseline to 18 months post ACLR 	This trial is designed to evaluate whether NMES and ECC can improve quadriceps strength. Thus, quadriceps strength at 9 months (when participants return to activity) and 18 months (longer-term assessment).

4 STUDY DESIGN

4.1 OVERALL DESIGN

In order to determine whether high intensity NMES +ECC can improve quadriceps strength better than the current standard of care (NMES placebo + ECC placebo) (primary objective), we propose a comparative effectiveness, single-center, randomized, double-blind, parallel group, placebo-controlled trial of NMES and ECC in patients with ACLR. One-hundred twelve participants scheduled to undergo an ACLR will be randomized into one of two study arms: 1) NMES + ECC ; or 2) NMES placebo + ECC placebo. All participants regardless of assignment will undergo standard of care ACL rehabilitation that focuses on minimizing effusion, restoring range of motion, and improving muscle strength (standard concentric exercises). The study intervention duration is 14-18 weeks, with NMES and NMES placebo beginning within 2 weeks of the ACLR and is provided twice/week for 8 weeks and ECC and ECC placebo beginning 6-10 weeks post-ACL surgery and is provided twice/week for 8 weeks.

Additionally, 28 patients will be enrolled into a control group where no study interventions are provided and participants will be followed and tested as they undergo physical therapy as prescribed by their treating physician. These patients are eligible for the study but refuse to participate in the randomized controlled trial however, they are willing to participate in the study procedures to provide efficacy measures.

We will randomize participants to treatment groups using minimization, a method of unbiased allocation ensuring balance across stratification factors: meniscal injury and treatment, articular cartilage injury (described below), sex and graft type. (See section 6. 3 for details on the randomization method using the minimization method.)

Our primary outcomes will be examined at three study time points: 1) pre-ACLR (within 2 weeks prior), 2) 9 months post-ACLR (± 2 weeks), and 3) 18 months post-ACLR (± 2 weeks). MRI and X-ray measures will be collected at 18 months post-ACLR, biomechanical measures at 9 and 18 months post-ACLR, hop testing at 9 and 18 months post-ACLR and questionnaires at all 3 time points. Additionally, we will examine change in quadriceps muscle strength and muscle volume from baseline to post-NMES intervention (testing visit 2) and post-ECC intervention (testing visit 3) in an attempt to understand the effects of the individual components of the combined NMES+ECC intervention.

4.2 SCIENTIFIC RATIONALE FOR STUDY DESIGN

A double-blind, parallel group, placebo-controlled randomized clinical trial assessing the superiority of NMES and ECC will be utilized. This design was chosen to assess whether our multimodal intervention (NMES + ECC) is superior to the placebo arm. An independent group of participants will receive only the standard of care rehabilitation therapy to assess the ability of reducing the intensity of NMES and ECC to achieve a “true” placebo. This additional non-randomized group strengthens the study by confirming the sham NMES & ECC procedures can serve as “true” placebos.

4.3 JUSTIFICATION FOR DOSE

Neuromuscular Electrical Stimulation: Patients randomized into the NMES + ECC arm will receive NMES 2x/week for 8 weeks following ACLR, beginning 0-2 weeks post-operative. For the first two weeks, NMES will be delivered in the clinic by the patients' physical therapist. The treatment intensity for the first two weeks will be set to the maximum tolerated by the patient, but all other stimulation parameters will remain the same as outlined for the remaining 6 weeks of NMES intervention. For the last 7 weeks of NMES treatment, patients will be positioned in a dynamometer with their hips flexed to 90° and ACL knee flexed to 60°. Stimulating electrodes will be placed over the vastus lateralis proximally and the vastus medialis distally. An electrical stimulator (Vectra Neo, DJO Global, Vista, CA) will be set to deliver a 2500 Hz alternating current, modulated at 75 bursts/s, with a ramp-up time of 2-seconds, followed by a 50-second rest period. Fifteen isometric actions lasting 10 seconds each will be elicited during each session. The treatment intensity will be set at a minimum intensity (higher if tolerated) to achieve a maximum voluntary isometric quadriceps contraction (MVIC) in the injured limb that is equivalent to an MVIC of 40% of the contralateral side. **Justification for Dose:** Dose response curves from previous work show that in order to recover ~70% of isometric quadriceps strength, NMES needs to be delivered at an intensity that will elicit 40% of the contralateral MVIC.

NMES placebo. Participants randomized to the NMES placebo + ECC placebo arm will receive an NMES placebo intervention 2x/week for 8 weeks following ACLR, beginning 0-2 weeks post-operative (to mimic the timing associated with the NMES intervention). The NMES placebo will utilize the same equipment and follow the same protocol as in the actual NMES intervention, with the exception that the intensity of the current will be set lower in the last 6 weeks of NMES intervention. The treatment intensity will be set at an intensity to achieve a MVIC of 15% of the injured side. In the first 2 weeks of NMES treatment will be delivered at max tolerated by the patient as is done for the NMES active arm. **Justification for Dose:** In our pilot work, electrical stimulation of this intensity does not result in improvements in muscle strength; as such it is a fitting placebo for the current trial.

High-Intensity Eccentric Exercise (ECC): Participants randomized into the NMES + ECC arm will receive ECC 2x/week for 8 weeks, beginning between 6 - 10 weeks post-ACLR when adequate quadriceps control is achieved, determined by the participant's physician. To perform the ECC, patients will be positioned in a BLAST!™ Leg Press (BioLogic Engineering Inc.) with their ACLR knee range of motion limited to 20 to 60° of knee flexion. Patients will perform warm-up trials consisting of 10 concentric and eccentric quadriceps actions with the ACLR limb. Following the warm-up trial, each participant will perform 10 isokinetic eccentric quadriceps actions with the ACLR limb. In total for each session, patients will complete 4 sets of 10 leg press actions with 2-minute rests between each set. During the eccentric actions, patients will train at an eccentric intensity equal to 70-90% of their one-repetition maximum (this will be recorded at the beginning of each week), and a concentric intensity equal to 40% of their one repetition maximum. **Justification for Dose:** In our pilot work^{35,37}, using an eccentric intensity identical to that described above, patients, on average, realized a 90% improvement in quadriceps strength over 6 weeks (which is shorter than the 8 weeks implemented in this study).

ECC placebo: Participants randomized to the NMES placebo + ECC placebo arm will receive an ECC placebo intervention 2x/week for 8 weeks, beginning at 6 - 10 weeks following ACLR. ECC placebo will utilize the same equipment and follow the same protocol as in the actual eccentric intervention, with the exception that the eccentric training intensity the patients will use

is lower. Rather than training at 70-90% of their MVIC, patients will train at 40%. This intensity is too low to generate increases in muscle strength. **Justification for Dose:** In our pilot work, eccentric exercise of this intensity does not result in improvements in muscle strength; as such, it is a fitting placebo for the current trial.

Standard of Care: All participants, both those receiving study intervention (i.e. NMES + ECC or NMES placebo + ECC placebo) or in the SOC control group, will receive standard of care physical therapy post-ACLR. The SOC control group will provide confidence that the intensity of NMES and ECC in the placebo group is sufficiently low.

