Exploratory Endpoints: Change from baseline to 9 months and to 18 months post-ACLR in isokinetic quadriceps strength symmetry index.

Study Population: 150 patients who have sustained a unilateral ACL injury between the ages of 14-45 years will be consented. Of those, 122 participants will be randomized to one of the two treatment groups; 10 of those participants will be removed from analysis due to the COVID-19 pandemic. 28 participants will be enrolled (not randomized) to the SOC Control group.
III

[figure not shown]
Phase:
Description of Sites/Facilities The University of Michigan
Enrolling Participants:
Description of Study Interventions: This study combines the following interventions into two randomized treatment arms:
NMES: defined as delivery of high-intensity neuromuscular electrical stimulation (NMES) beginning in weeks 0-2 post-ACLR and continuing for 8 weeks.
ECC: defined as delivery of eccentric exercise (ECC) at 70-90% of the 1 RM (repetition maximum) beginning between the 6th-10th week post-operative until the 14-18th week post-operative.
NMES placebo: defined as delivery of low-intensity neuromuscular electrical stimulation (NMES) beginning in weeks 0-2 post-ACLR and continuing for 8 weeks.
ECC placebo: defined as delivery of eccentric exercise (ECC) at 15% of the 1 RM (repetition maximum) beginning between the 6th-10th week post-operative until the 14-18th week post-operative.

The treatment groups to which participants will be randomized are:
(1) NMES + ECC
(2) NMES placebo + ECC placebo

[figure not shown]
There will also be a SOC Control group in which participants receive no study-related treatment or placebo outside of their standard of care physical therapy.

Study Duration: 5 years
Participant Duration: Approximately 20 months from the time the consent form is signed
Estimated Time to Complete Enrollment: 5 years

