NMES placebo. Participants randomized to NMES placebo + ECC placebo will receive an NMES placebo intervention 2x/week for 8 weeks following ACLR, beginning 0-2 weeks post-operative (to mimic the timing associated with the NMES intervention). Similar to the NMES intervention group, for the first two weeks NMES will be delivered in the clinic by the participants' physical therapist. The treatment intensity for the first two weeks will be set to the maximum tolerated by the participant, but all other stimulation parameters will remain as outlined below for the last 6 weeks. The NMES placebo will utilize the same equipment and follow the same protocol as in the actual NMES intervention, with the exception that the intensity of the current will be set lower. The treatment intensity will be set at an intensity to achieve a MVIC of 15% of the injured side.

High-Intensity Eccentric Exercise (ECC): Participants randomized into the NMES + ECC group will receive ECC 2x/week for 8 weeks, beginning between 6 - 10 weeks post-ACLR when adequate quadriceps control is achieved. To perform the ECC, participants will be positioned in a BLAST!™ Leg Press (BioLogic Engineering Inc.) with their ACLR knee range of motion limited to 20 to 60° of knee flexion. Participants will perform warm-up trials consisting of 10 concentric and eccentric quadriceps actions with the ACLR limb. Following the warm-up trial, each participant will perform 10 isokinetic eccentric/concentric quadriceps actions with the ACLR limb. In total for each session, patients will complete 4 sets of 10 eccentric/concentric actions with 2-minute rests between each set. During the eccentric actions, participants will train at an intensity equal to or greater than 70-90% of their concentric one-repetition maximum (this will be recorded at the beginning of each week). Concentric intensity will be set at 40% of the one-repetition maximum. **Dose Changes:** Treatment intensity will be set at the beginning of each week to ensure strength gains achieved during the study period are reflected in the dose delivered. The timing of initiation eccentric exercise will be evaluated on a patient-by-patient basis. It will begin when the patient has adequate quadriceps control to handle this type of training and will be determined by the physical therapist working with the participant and their physician.

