ECC placebo: Participants randomized to NMES placebo + ECC placebo will receive an ECC placebo intervention 2x/week for 8 weeks, beginning at 6 - 10 weeks following ACLR. ECC placebo will utilize the same equipment and follow the same protocol as in the actual eccentric intervention, with the exception that participants will train eccentrically at 10% of their MVIC.

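### The eccentric load of the placebo arm is given as 15% of 1RM, 40% with no base restated, and 10% of MVIC, and nothing says which governs

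*Combined protocol and SAP*

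**What the plan says.** **Placebo arm.** Three current sections set the eccentric load:

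- Section 1.1 (Synopsis): "ECC placebo: defined as delivery of eccentric exercise (ECC) at 15% of the 1 RM (repetition maximum").
- Section 4.3: "Rather than training at 70-90% of their MVIC, patients will train at 40" per cent. The figure has no base of its own; the same sentence expresses the active load in MVIC.
- Section 6.1.2: "participants will train eccentrically at 10% of their MVIC".

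Straight after its 40% figure, section 4.3 adds: "This intensity is too low to generate increases in muscle strength". Its dose justification then says: "In our pilot work, eccentric exercise of this intensity does not result in improvements in muscle strength".

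**Active arm.** The Synopsis has "ECC: defined as delivery of eccentric exercise (ECC) at 70-90% of the 1 RM (repetition maximum"). The ECC paragraph of 4.3 agrees: "patients will train at an eccentric intensity equal to 70-90% of their one-repetition maximum". The ECC placebo paragraph of 4.3 refers to the same 70-90% as a share of MVIC. Section 6.1.2 has "participants will train at an intensity equal to or greater than 70-90% of their concentric one-repetition maximum".

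**Use of the load.** Section 6.3 prescribes 32 sessions, 16 of them ECC or its placebo. It records eccentric intensity on case report forms and counts the sessions delivered at the recommended dose.

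**The concern.** The placebo arm is the only randomized comparator, and its eccentric intensity is half of what makes it a placebo. A therapist following one section would depart from another.

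Three things depend on a single definition:

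- **The justification.** The claim that the placebo load does not build strength is made for one of the three figures only.
- **The dosage-adherence count in 6.3.** It cannot be scored in the placebo arm until the recommended dose is fixed. In the active arm, a session above 90% of 1RM fits 6.1.2 but not the Synopsis or the ECC paragraph of 4.3.
- **The exploratory comparison with the standard-of-care group.** It asks whether lowering the NMES and ECC intensity gives a genuine placebo, so it needs to say what the lowered intensity was.

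**Working it through.** **1. The nearest calculated figure in the plan.** The placebo load is a stated setting, not a derived number. The only derived figure nearby is the power in section 9.2: effect size 0.7, 45 per group after 20% drop-out (56 × 0.8 = 44.8), two-sided 0.025 per endpoint.

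- Normal approximation: 0.7 × √(45/2) = 3.320; 3.320 − 2.241 = 1.079; power = Φ(1.079) = 0.860.
- Noncentral t: 0.849.

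Both agree with the stated minimum of 80%. Nothing in this point changes that calculation.

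**2. The sections side by side.**

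| Place | Placebo eccentric load | Active eccentric load |
|---|---|---|
| 1.1 Synopsis | 15% of 1RM | 70-90% of 1RM |
| 4.3, ECC paragraph | – | 70-90% of 1RM |
| 4.3, ECC placebo paragraph | 40%, base not restated | 70-90% of MVIC |
| 6.1.2 | 10% of MVIC | at or above 70-90% of concentric 1RM |

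None of these is amendment-log text. No section ranks the others. The study manual is cited for MRI positioning and sequences (8.1), data collection procedures (10.1.9.1) and deviations (10.1.10), but not for this load.

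**3. Can a reading of the 40% remove the conflict?**

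- Read as MVIC, the natural reading: 40/10 = 4.0 times the 6.1.2 figure.
- Read as 1RM: 40/15 = 2.67 times the Synopsis figure.

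Each reading leaves a conflict on a common scale. The 15% of 1RM and the 10% of MVIC cannot be compared, because the documents give no conversion.

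**4. Implied contrast between arms (active ÷ placebo).**

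- Synopsis: 70/15 = 4.67 to 90/15 = 6.0.
- 4.3, only if the 40% shares the base of the 70-90%: 70/40 = 1.75 to 90/40 = 2.25.
- 6.1.2: not computable, since the active load is on 1RM and the placebo load on MVIC.

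**5. Effect on the adherence count.** ECC is 2 sessions a week × 8 weeks = 16 of 32 sessions (50%). Section 6.3 gives no tolerance, so assume that a session counts only at the stated load and that a participant's load is constant.

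- At 15% of 1RM throughout: 16/16 under the Synopsis, 0/16 under 4.3 read as 1RM.
- At 10% of MVIC throughout: 16/16 under 6.1.2, 0/16 under 4.3 read as MVIC.

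This is a worst-case bound under those assumptions. It does not estimate how many sessions would be misclassified.

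**The case against.** - **6.1.2 is the dosing section, so it governs.** That is a reasonable instinct, but the protocol does not say so. If it did govern, the pilot justification in 4.3 would belong to a different figure, and 6.1.2 would still put the two arms on different scales.
- **The 40% may come from the concentric setting.** Sections 4.3 and 6.1.2 both set the concentric intensity of active ECC at 40% of 1RM. This could explain where the number came from, and whoever reconciles the text should know it. The placebo sentence in 4.3 is about eccentric intensity, however, so the conflict stands as written.
- **The pilot claim may cover the lower figures.** On any shared base, 40% is the highest placebo value, so by the protocol's own reasoning a lower value on that base is no less inert. That stands. The gap that remains is across bases, where no conversion is given. The standard-of-care group offers some check, but it is non-randomized and exploratory.
- **The consequence is limited.** This is largely correct. The adherence count is descriptive, and no analysis in section 9 is stated to use it. The scoring rule may also be in the separate SAP that section 9.4 announces. The case for correction rests on the comparator's definition rather than on the session arithmetic.
- **The active-load differences are secondary.** Naming the 1RM as concentric may only clarify it. The MVIC wording in 4.3 and the open upper limit in 6.1.2 are real discrepancies, but smaller than the three-way placebo conflict.

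**Conclusion.** The contradiction holds and must be corrected. Current text gives three placebo loads on at least two scales. They differ 4-fold if the 40% means MVIC, or 2.7-fold if it means 1RM, and no reading reconciles them. The active load is also stated inconsistently. Up to 16 of 32 sessions in the dosage count depend on which section is used, assuming no tolerance and a constant delivered load.

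The limits are equally clear. The primary modified intention-to-treat analysis goes by assigned treatment (9.3, 9.4.2) and is unaffected, as is the stated power. The documents do not show that different loads were delivered. The defect lies in what the protocol specifies. This review does not say which intensity or reference measure is right.

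**What to change.** 1. Reconcile the Synopsis, 4.3 and 6.1.2 to one ECC intensity and one reference measure per arm, and make clear whether the active range has an upper limit.
2. Tie the pilot justification in 4.3 to the reconciled placebo value.
3. Define the recommended dose in 6.3 by reference to those values, with the scoring rule and any tolerance. If sessions were delivered under a different instruction, say which one was in force.
4. Report delivered ECC intensity per session by randomized arm from the existing case report forms. Section 6.3 does not give the base on which eccentric intensity is recorded, so the table should state it.

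The cost is protocol wording and one descriptive table. The intensity data are already being collected. Sample size, analysis sets and the primary model do not change. A single-scale table depends on the base used on the forms, which should be checked first.
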